7.5.1. Baseline

The frequency of variant of baseline genetic variations, i.e. the number of subjects with baseline genetic variations, will be tabulated in frequency outputs (n, %), based on NGS data (1% and 15% cut-off), and the genetic variations will be listed for all subjects.

Subgroup analysis by the presence of baseline genetic variations will be tabulated to evaluate the impact on treatment efficacy (efficacy categories including but not limited to functional cure, partial cure, treatment failure).

7.5.2. Post-Baseline

- Time of Virologic Breakthrough (if applicable)

For subjects with virologic breakthrough, the incidence of treatment-emergent (NGS) and treatment enriched genetic variations (with primary focus on substitutions) will be tabulated in

frequency outputs (n, %) and the genetic variations will be listed for all subjects with paired baseline and post-baseline sequencing data.

The return to baseline for subjects with virologic breakthrough and treatment-emergent genetic variations at time of virologic breakthrough will be tabulated in frequency outputs based on NGS data, as well as the treatment-emergent genetic variations in subjects who did not return to baseline.

- Time of End of Treatment

For subjects who don't meet the NA treatment completion criteria, the incidence of treatment-emergent and treatment-enriched variants (with primary focus on substitutions) will be tabulated in frequency outputs (n, %) and the genetic variations will be listed for all subjects with paired baseline and post-baseline sequencing data.

The return to baseline for subjects who don't meet the NA treatment completion criteria and treatment-emergent genetic variations end of treatment will be tabulated in frequency outputs based on NGS data, as well as the treatment-emergent genetic variations in subjects who did not return to baseline.

- Time of Virologic /Clinical Flare (if applicable)

For subjects with virologic/clinical flare, the incidence of treatment-emergent (NGS) and treatment-enriched genetic variations (with primary focus on substitutions) will be tabulated in frequency outputs (n, %) and the genetic variations will be listed for all subjects with paired baseline and post-baseline sequencing data.

The return to baseline for subjects with virologic/clinical flare and treatment-emergent genetic variations at time of virologic/clinical flare will be tabulated in frequency outputs based on NGS data, as well as the treatment-emergent genetic variations in subjects who did not return to baseline.

- Time of Re-treatment during Post-treatment Follow-up

For subjects who meet re-treatment criteria during follow-up, the incidence of treatment-emergent and treatment-enriched variants (with primary focus on substitutions) will be tabulated in frequency outputs (n, %) and the genetic variations will be listed for all subjects with paired baseline and post-baseline sequencing data.

The return to baseline for subjects who meet re-treatment criteria during follow-up and treatment-emergent genetic variations at time of meeting the re-treatment criteria will be tabulated in frequency outputs based on NGS data, as well as the treatment-emergent genetic variations in subjects who did not return to baseline.

- Other Post-Baseline

The frequency of variant of genetic variations at other time points will be tabulated in frequency outputs (n, %), based on NGS data (1% and 15% cut-off), and the genetic variations will be listed for all subjects. Time points of specific interest are end-of-treatment, time point of re-treatment, and end-of-study.

7.5.3. Over the Study Period

For all subjects, listings with relevant baseline disease and demographic characteristics, session info, all genetic variations at baseline, at time of virologic breakthrough (if applicable), at end of study treatment, and at end of study will be generated.

For all subjects, listings with relevant baseline disease and demographic characteristics, session info, and aggregate post-baseline sequence data over the whole treatment period, and aggregate post-baseline sequence data over the whole study period will be generated.

7.6. HBV genotype

Plasma samples for HBV genotyping were taken at screening and tested using the INNO-LiPA HBV genotyping assay. In addition, plasma samples were taken at baseline to determine the HBV genotype using the HBV full genome sequence and phylogenetic analysis.

The number and percentage of subjects by HBV genotype for study analysis will be tabulated. In addition, cross-tabulations per HBV genotype will compare the HBV genotypes determined by the INNO-LiPA HBV genotyping assay and by using the HBV full genome sequence.

8. PHARMACOKINETICS/PHARMACODYNAMICS

8.1. Pharmacokinetics

Two types of PK analyses will be conducted, including noncompartmental analysis in the PK sub-study participants and population PK analysis in all participants. Details of the PK analyses will be described in a separate analysis plan and results will be reported separately.

8.2. Pharmacokinetic/Pharmacodynamic Relationships

Relationships of PK parameters for JNJ-3989, JNJ-6379, and/or NAs (ETV, TAF and/or TDF), as applicable, with selected efficacy and with selected safety endpoints will be evaluated, applying graphical tools and, if feasible, statistical models.

Modeling of key pharmacodynamic parameters (e.g. HBsAg, HBV DNA) may be performed using population pharmacokinetics/pharmacodynamics (PK/PD). Details of the PK/PD analyses will be described in a population PK/PD analysis plan and results will be presented in a separate report.

8.3. Immune Response

Descriptive statistics (for example, may include n, mean, SD, CV, geometric mean, median, minimum, and maximum) will be used to describe the magnitude of the IFN- γ T cell response or the CD4+ and CD8+ T-cell responses (expressing at least 1 cytokine such as IL-2, TNF- α or IFN- γ specific to any HBV antigen) as defined by ELISpot and/or ICS, respectively. Changes from baseline (if present) will also be tabulated for PBMCs during study intervention and follow-up. The proportion (%) of CHB participants with positive responses based on the magnitude of the IFN- γ T cell response or the CD4+ or CD8+ T cells expressing at least 1 of the cytokines amongst IL-2, TNF- α or IFN- γ for 1 of the HBV antigens as defined by ELISpot and/or ICS, respectively, will be determined.

Graphs showing the individual subject values as dots, together with horizontal lines indicating the corresponding median and interquartile range (IQR) per time point for each assay will be presented. The spaghetti plots will be used to show the patient profiles per time point for each assay. A graph showing the median and IQR over time by intervention arm will be presented. A bar chart will be used to show the breadth of response (i.e. HBV-specific immune response rate for combinations of peptide pools).

For intracellular cytokine staining (ICS), for all cytokine combinations (IFN γ and/or TNF α and/or IL-2), pie charts will be presented to reflect the distribution of each of the cytokine combinations (i.e. the proportion of a specific cytokine combination of the CD4 or CD8 T-cells secreting at least one cytokine), and bar charts will be presented to reflect the mean magnitude of each combination.

9. PATIENT-REPORTED OUTCOMES

The impact of study intervention on participants' HRQoL, self-stigma level, and impression of change will be assessed using PROs at predefined time points. The following PRO instruments will be used: the HBQOL scale, an HBV-specific self-stigma PRO scale, and the PGIC scale. All PRO analyses will be performed using the ITT analysis set.

9.1. Hepatitis B Quality of Life Instrument (HBQOL)

The HBQOL version 1 is a 31-item disease-specific instrument designed to measure HRQoL for participants with CHB.

Each item is scored on a 5-level response scale ranging from 1 through 5. Each response is transformed along a 0 to 100-point scale, where lower scores denote less HRQOL impact, and higher scores denote more HRQOL impact (i.e. 0=best score; 100=worst score), as follows:

Level 1 – 0 points

Level 2 – 25 points

Level 3 – 50 points

Level 4 – 75 points

Level 5 – 100 points

The items are combined to form 7 subscales, as follows:

Psychological Well-Being (8 Items)

- Anxious (F6)
- Frustrated (F4)
- Sad (F3)
- Angry (F7)
- Less Enjoyable (F10)
- Scared (F13)

- Bad (F9)
- Isolated (F8)

Anticipation Anxiety (6 Items)

- Concern Failure (C1)
- Concern Cancer (C2)
- Concern Worsen (C15)
- Concern Serious (C12)
- Concern Survival (C9)
- Concern Flare (C5)

Vitality (5 Items)

- Tiredness (P1)
- Worn Out (F5)
- Muscle Aches (P3)
- Memory Problems (P2)
- Unproductive (F12)

Stigma (6 Items)

- Concern Embarrassed (C14)
- Ashamed (F1)
- Concern Self-Conscious (C10)
- Concern Socially Isolated (C11)
- Concern Boss (C3)
- Stigmatized (F2)

Vulnerability (3 Items)

- Concern Eat (C13)
- Concern Sick Easily (C6)
- Concern Medicines (C8)

Transmission (3 Items)

- Concern Transmit Sex (C7)
- Concern Transmit Child (C4)
- Sex Difficult (F11)

Viral Response (4 Items)

- Concern Transmit Sex (C7)
- Concern Transmit Child (C4)
- Concern Eat (C13)
- Concern Medicines (C8)

Each subscale score is simply calculated as the average score among the items included in that subscale. In addition to the 7 subscales, there is a single global score that reflects the results on all 31 items. The global score is the average score among all the items in the HBQOL. Responses are transformed along a 0 to 100-point scale, where lower scores denote less HRQoL impact, and higher scores denote more HRQoL impact (ie, 0=best score; 100=worst score).

For example, consider these sample scores for items in the vulnerability scale:

Item Number	Item Name	Raw Score	Scaled Score
C13	Concern eat	2	25
C6	Concern sick easily	4	75
C8	Concern medicines	3	50
		Average	50

The score on this subscale is 50 out of a possible score of 100, where higher scores denote more severe negative impact of HBV on HRQOL.

Descriptive statistics of the actual values and change from baseline values at each timepoint (including baseline and available analysis time point) for the derived scores will be displayed for subscales/domains and global score by intervention arm. The proportion of participants experiencing a clinically important improvement or worsening from baseline (if applicable) at each timepoint will be calculated by intervention arm. Analyses will also be performed on the changes from baseline at specific time points (Week 48, 72, 96, etc.) as appropriate for different subgroups: participants who meet the NA treatment completion criteria at Week 48 versus those who do not, and participants with versus participants without HBsAg seroclearance 24 weeks and 48 weeks after completion of all study intervention at Week 48.

In addition, effect sizes will be calculated to measure the magnitude of difference between means in all different intervention arms using an ANCOVA, with intervention arm, and 2 randomization stratification factors, as main effect in the model, and the two 2-way intervention arm-stratification factor interaction terms, and baseline as covariate. The LS means of the change from baseline on the analysis time points with estimates, SE, 90% CI, p-values will be presented. A graphical representation may be used to display the adjusted mean change from baseline.

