1.4. Sample Size Justification

The total study sample size is 450 participants with a 2:2:2:2:1:1 randomization ratio, where 90 participants will be randomly allocated to each of the arms including a JNJ-3989 dose (Arms 1 to 4) and 45 participants will be randomly assigned to each of the arms with no JNJ-3989 component (Arms 5 and 6). Due to the global impact of the pandemic Coronavirus Disease 2019 (COVID-19) and the use of the modified ITT analysis set as primary set for the efficacy analyses, study enrollment was extended by approximately 5% of participants.

Statistical power to test a dose-response signal (max trend test) was assessed using the generalized version of the MCP-Mod ([Pinheiro J. et al., 2014](#)) applied to the binary primary efficacy endpoint on the logit scale using data from Arms 2, 3, and 4 (JNJ-3989 at 200, 100, and 40 mg dose, respectively +NA), and Arm 6 (placebo+placebo+NA) as control. The “max trend test” is to test the null hypothesis that none of the doses is better than control (i.e. the flat dose response curve). The power to reject the null hypothesis is $\geq 85\%$ under all 5 candidate dose-response models for an absolute response rate of the highest dose of JNJ-3989 of at least 25% (one-sided alpha level of 5%). In addition, assuming a response rate of 5% in control Arm 6, the study sample size provides a statistical power $\geq 84\%$ to detect a difference of $\geq 20\%$ in the primary endpoint between Arm 1 and Arm 6, and power $\geq 76\%$ for at least a 20% delta between Arm 5 and Arm 6, using a fixed sequence approach for controlling for multiplicity.

The testing among the regimens (Arm 1, 3, and 5) will be performed using the min test approach control for the one-sided Type 1 error of 0.05. The chosen study sample size and randomization allocation provides acceptable power levels also for the comparison of different combination regimens, ie, JNJ-3989+JNJ-6379+NA (Arm 1, 100-mg dose of JNJ-3989) versus JNJ-3989+NA (Arm 3, 100-mg dose of JNJ-3989), and versus JNJ-6379+NA (Arm 5), respectively. For example, for the same delta of 25% between Arm 1 and Arm 3 and between Arm 1 and Arm 5, the power to conclude that Arm 1 is statistically superior to Arm 3 and Arm 5 is 87%, assuming a response rate of 25% in both Arm 3 and 5. Details are provided in Section 9 of the protocol Amendment 1.

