1.5. Randomization and Blinding

Randomization

Central randomization is implemented in this study. Participants are randomly assigned to 1 of 6 intervention arms with a ratio of 2:2:2:2:1:1 (Arms 1:2:3:4:5:6). The randomization is stratified by HBeAg status at screening (positive versus negative) and by treatment history (not currently treated versus virologically suppressed).

Blinding

At Week 48 or earlier at the time of treatment discontinuation, it will be communicated to the investigators whether the participants were allocated to either an intervention arm (Arms 1 to 5) or the control arm (Arm 6) to determine which follow-up visit schedule will be followed. Only at Week 72, randomization codes (for Arms 1 to 5) will be fully disclosed to the investigators. The sponsor will be fully unblinded at the time of the primary analysis (all participants have completed Week 48 or discontinued early).

Sponsor personnel involved in the pharmacokinetic and pharmacodynamic modelling will have access to the pharmacokinetic and pharmacodynamic data before formal unblinding for the primary analysis. Sponsor personnel involved in trial conduct, data management, and statistics will not have access to these data prior to the primary analysis. The sponsor will be fully unblinded at the time of the primary analysis which will be conducted at the time when all participants have completed Week 48 or discontinued earlier.

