5.5. Exploratory Endpoints

5.5.1. Changes in Fibrosis

To explore the changes in the severity of liver disease at the end of follow-up versus screening/baseline, the changes in fibrosis (according to Fibroscan liver stiffness measurements) will be summarized using descriptive statistics (for example, may include n, mean, SD, 90% CI, median, minimum, maximum) by intervention arm. The comparison among intervention arms will

be done using ANCOVA with intervention arm, randomization stratification factors as main effects in the model and baseline score as covariate.

At each assessment time point, a frequency distribution of severity scores will be produced by intervention arm. A graphical display will also illustrate the findings.

Waterfall plots for changes from baseline of fibrosis will also be presented.

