9.2. HBV-specific Self-stigma PRO Scale

The HBV-specific self-stigma scale is an hepatitis B-specific PRO instrument designed to assess the experience and impact of self-stigma. The current version consists of 37 items. The items cover aspects of self-stigma such as a) devaluation, inferiority, and worthlessness, b) marginalization and alienation, c) secrecy and concealment, d) shame and guilt, and e) withdrawal and social

isolation. Each of the 37 items is graded on a 5-point Likert scale (1=“Never”, 2=“Rarely”, 3=“Sometimes”, 4=“Often”, and 5=“Always”).

The analyses will be performed in a similar manner as described in Section 9.1.

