9.3. Patient Global Impression of Change Scale (PGIC)

The PGIC scale is a single-item PRO scale aimed at assessing the participant’s perceptions of change (improvement or worsening) in how they feel overall compared to the beginning of the study. Response options include: “Much better”, “Better”, “A little better”, “No change”, “A little worse”, “Worse”, “Much worse”.

The tabulation of the number and percentage of participants at each response level will be displayed per time point for each intervention arm. The comparison among the intervention arms will be done using Mann–Whitney U test.

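### The HBQOL and self-stigma ANCOVA leaves the weighting of LS means over strata unstated, which can cost precision, and the PGIC comparison is unstratified with no pairs named

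*SAP*

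**What the plan says.** For HBQOL, SAP 9.1 states that "effect sizes will be calculated to measure the magnitude of difference between means in all different intervention arms using an ANCOVA". The model has arm and the two stratification factors as main effects, "and the two 2-way intervention arm-stratification factor interaction terms, and baseline as covariate". The output is inferential: "The LS means of the change from baseline on the analysis time points with estimates, SE, 90% CI, p-values will be presented". Nothing is said about the weights used to average over strata.

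For the self-stigma scale, SAP 9.2 says: "The analyses will be performed in a similar manner as described in Section 9.1".

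For PGIC, SAP 9.3 says: "The comparison among the intervention arms will be done using Mann–Whitney U test". It names no pairs, no global test and no stratification.

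For comparison, SAP 5.5.1 analyses change in fibrosis by "ANCOVA with intervention arm, randomization stratification factors as main effects in the model and baseline score as covariate", with no arm-by-factor terms.

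**The concern.** Once arm-by-factor interactions are in the model, there is no single arm difference. There is one per stratum, and the reported LS-mean difference is an average whose weights must be chosen. Conventional LS means give each level of a factor equal weight: half HBeAg-positive and half negative, half untreated and half suppressed. The trial does not plan to enrol that mix. Protocol 6.3 aims for 40% not currently treated, with 40% of those expected to be HBeAg-positive. An equal-weight average leans on the smallest cells and loses precision. An average over the observed mix does not. Two programmers following SAP 9.1 could therefore report different estimates, standard errors and p-values.

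For PGIC, Mann-Whitney compares two groups. Six arms give 15 possible pairs at each time point, and the SAP does not say which are meant. The test also ignores both randomisation factors. PGIC has no baseline score to adjust for, so the strata are the natural adjustment.

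**Working it through.** The documents give no standard error, power or sample size for the PROs, so there is no stated figure to reproduce.

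**Inputs**
- "The total study sample size is 450 participants with a 2:2:2:2:1:1 randomization ratio" (SAP 1.4), so 450 × 2/10 = 90 in Arms 1 to 4 and 450 × 1/10 = 45 in Arms 5 and 6.
- Not currently treated: T = 0.40. HBeAg-positive among them: 40%, so 0.16 of the total (Protocol 6.3).
- HBeAg-positive share among suppressed participants, q: not given. Assumed 10% to 40%, with 5% and 50% as outer values.
- Equal residual SD in both models, baseline balanced across arms, strata balanced across arms, full arm sizes.

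**ANCOVA.** With both two-way interactions, each arm has its own additive model in the two factors. For an LS mean evaluated at weights w, the variance of an arm difference relative to the main-effects model is

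ratio = 1 + d′S⁻¹d,

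where d = w minus the enrolled proportions and S is the covariance matrix of the two factor indicators.

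Take q = 20% with equal weights:
- HBeAg-positive overall: E = 0.16 + 0.60 × 0.20 = 0.28.
- d = (0.5 − 0.40, 0.5 − 0.28) = (0.10, 0.22).
- Variances: 0.40 × 0.60 = 0.24 and 0.28 × 0.72 = 0.2016. Covariance: 0.16 − 0.40 × 0.28 = 0.048.
- Determinant: 0.24 × 0.2016 − 0.048² = 0.04608.
- d′S⁻¹d = (0.10² × 0.2016 − 2 × 0.10 × 0.22 × 0.048 + 0.22² × 0.24) / 0.04608 = 0.01152 / 0.04608 = 0.25.
- Variance ratio 1.25; SE ratio √1.25 = 1.118.

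The same steps at other values of q:

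| q | HBeAg-positive overall | Variance ratio | Rise in SE |
|---|---|---|---|
| 10% | 22% | 1.458 | 21% |
| 20% | 28% | 1.250 | 12% |
| 30% | 34% | 1.143 | 7% |
| 40% | 40% | 1.083 | 4% |

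The outer values give a rise of 28.4% at q = 5% and 2.6% at q = 50%.

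For 90 versus 45, the main-effects SE is √(1/90 + 1/45) = 0.183 SD. At q = 20% the equal-weight interaction SE is 0.183 × 1.118 = 0.204 SD.

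With observed-margin weights d = 0, so the ratio is 1.000 at every q. In practice d would be near zero rather than exactly zero, because randomisation balances the strata only approximately.

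The loss comes from thin cells. A 45-participant arm has 0.16 × 45 = 7.2 untreated HBeAg-positive participants and, at q = 20%, 0.60 × 0.20 × 45 = 5.4 suppressed HBeAg-positive participants. The PROs are collected only at sites with translations (Protocol 8.1.2), so actual cells may be smaller.

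**PGIC.** Pairs: 6 × 5 / 2 = 15 per time point. Two simulations compared the unstratified test with the van Elteren test at one-sided 0.05. The first used a seven-level outcome, 90 versus 45, and a latent shift of 0.45 SD, with 6,000 trials per scenario. The second set q = 20%.

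| Stratum effects | Quantity | Unstratified | Van Elteren |
|---|---|---|---|
| 0.5 SD each | Size, first run | 0.043 | 0.051 |
| 0.5 SD each | Power, first run | 70% | 74% |
| 0.5 SD each | Size, second run | 0.045 | 0.051 |
| 0.5 SD each | Power, second run | 71% | 73% |
| None | Power, first run | 74.4% | 73.9% |
| None | Power, second run | 75.1% | 74.6% |

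A separate null simulation of Arm 1 versus Arm 6 at two-sided 10% points the same way. Size was 9.5%, 7.5% and 6.7% when the strata explain 5%, 10% and 20% of the variance, and about nominal when they explain none.

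**The case against.** A reader might infer that the interaction model inflates every HBQOL and self-stigma standard error, or gives intervals wider than the data support. The documents do not support that. The inflation comes from equal weighting, which the SAP does not specify, and it vanishes with observed margins. Even under equal weights, the interval is valid for the contrast it estimates. Choosing between the two is a choice of target.

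A reader might also infer that SAP 9.1 mishandles the randomisation factors or departs from the SAP's own practice. Its ANCOVA adjusts for both factors. SAP 5.2.5 and 5.3.6 also derive arm estimates with 90% CIs from models containing both interactions, though there the purpose is subgroup exploration. Nor is PGIC the only unstratified comparison: the log-rank tests in SAP 5.4.3.3 and 5.4.14.2 are not described as stratified.

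For PGIC, a reader might conclude that the test is invalid. It is not: it can be run pair by pair, and ignoring the strata makes it conservative. The 0.5 SD stratum effects are assumed, and without them stratification costs a little power.

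Finally, the PROs are exploratory (Protocol 3), their scores are to be analysed descriptively (Protocol 9.4.1.5), and none enters the testing sequence in SAP 5.1.1. All of this stands and limits the point to low impact. It does not remove it: the SAP chose to report standard errors, intervals and p-values, and these need a defined average and named comparisons.

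**Conclusion.** The point holds in conditional form. SAP 9.1 and 9.2 leave the averaged arm difference undefined. The loss of precision is 4% to 21% in standard error under equal-weight LS means for q from 40% down to 10%, and nil under observed margins. The share q is an assumption, and the commitment in Protocol 6.3 to recruit enough HBeAg-positive suppressed participants argues against relying on the low end.

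For PGIC, the main gap is that the pairs are not named. The unstratified test is valid and costs about 2 to 4 points of power if each factor has an effect of about 0.5 SD. No dose or regimen test depends on these results, so this is a low-cost improvement rather than a threat to the trial's conclusions.

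**What to change.** - **SAP 9.1 and 9.2:** estimate arm differences from the SAP 5.5.1 model (arm, the two stratification factors as main effects, baseline), and keep the two interactions for a separate heterogeneity check. Alternatively, keep the present model and state that LS means use observed margins. Either choice removes the ambiguity and the possible loss of precision.
- **SAP 9.3:** replace the Mann-Whitney test with the van Elteren (stratified Wilcoxon) test by screening HBeAg status and treatment history. Name the pairs: each of Arms 1 to 5 versus Arm 6, Arm 1 versus Arm 3, and Arm 1 versus Arm 5.

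The cost is SAP wording and minor programming, plus about half a point of PGIC power if the strata are not prognostic. SAP Amendment 2 refers to interim analyses already done, and SAP 3.1 places these after the primary analysis, at which the sponsor is unblinded. The amendment should therefore record that the change was made after unblinding.
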